### 4. Aims of the study

Primary objective: to investigate the feasibility of conversion to lobectomy after neoadjuvant/induced chemoimmunotherapy in patients with operable non-small cell lung

cancer who are required to undergo pneumonectomy at first diagnosis (R0 resection rate).

Secondary objective: to investigate the perioperative and long-term outcomes of patients with operable non-small cell lung cancer who were evaluated to undergo pneumonectomy at first diagnosis and switched to neoadjuvant or induction chemoimmunotherapy and subsequent lobectomy.

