### **2.4.2 Assessment of potential risks/benefits**

It has been shown in retrospective studies that total pneumonectomy is only performed when lobectomy is difficult to achieve R0 resection and is associated with higher perioperative complications and mortality than lobectomy, with a significant impact on the patient's general state of health and strength scores, which may contribute to impaired long-term survival. In patients who do well on neoadjuvant or induction therapy, conversion to lobectomy can potentially reduce the incidence of perioperative adverse events, reduce the risk of immediate and long-term non-tumor death, protect the patient's general health and strength scores, and increase the patient's chances of receiving postoperative adjuvant therapy, thereby reducing the risk of tumor-related death.

Risk-minimizing measures: Select patients with good results of neoadjuvant or induction therapy according to strict admission criteria, review the tracheoscopic biopsy before surgery to clarify the status of the bronchus to be preserved, take frozen pathology to clarify the status of the nearest incision margins during the surgery to decide the actual surgical method, and maintain adjuvant therapy after the surgery to minimize the possibility of increasing the risk of local recurrence. Postoperatively, the patient's vital signs, drainage, and air leakage were closely observed to ensure perioperative safety.

Preoperative and intraoperative reassessment

1 Bronchoscopic biopsy of bronchial mucosa to be preserved/EBUS to assess the condition of the outer wall of the preserved bronchus.

2 In cases of main pulmonary artery invasion prior to neoadjuvant therapy, intraoperative

freezing is performed to assess the status of the arterial wall at the site of original invasion.

3 For cases with transverse fissure invasion, pulmonary fissure margins were frozen for pathologic evaluation.

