## **7. Research interventions**

### **7.1 Giving the research intervention**

#### **7.1.1 Description of the research intervention**

After the patients were enrolled in the group, further relevant examinations (bronchoscopy, chest enhanced CT, PET-CT (optional), cranial MR, cardiac ultrasound, pulmonary function, electrocardiogram, and blood test) were completed, contraindications to surgery were ruled out, and they were evaluated to receive neoadjuvant/induced chemo-immunotherapy after multidisciplinary discussion (thoracic surgery, respiratory medicine, pathology). After completion of treatment, the patient is reassessed and discussed multidisciplinary for surgical feasibility. Open or minimally invasive (thoracoscopic-assisted, robotic-assisted) radical lung cancer surgery with systemic lymph node dissection is performed, including

pneumonectomy, lobectomy, combined lobectomy, and sleeve lobectomy (with or without pulmonary angioplasty/sleeve). Based on the surgical pathology and guidelines, the postoperative adjuvant treatment and follow-up plan was individualized after multidisciplinary discussion.

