## 10. Statistical analysis

### 10.1 General methodology

All statistical analyses were performed using R software, and hypothesis tests were standardized using two-sided tests, giving the test statistic and its corresponding p-value.  $p<0.05$  was considered statistically significant, and 95% confidence intervals were set as required.

Statistical description: All indicators are described according to their nature. Qualitative indicators are expressed as frequencies and percentages of categories; metrics provide the number of cases, mean, standard deviation, median, minimum and maximum values.

Statistical inference: For overall survival time and disease-free survival time, overall survival curves and disease-free survival curves were plotted using the Kaplan-Meier method; risk differences between survival and disease-free survival were assessed using the Log-Rank test; multivariate analyses were performed using the Cox proportional risk model to assess the effect of subgrouping (surgical modality) and other prognostic factors on survival and disease-free survival. survival and disease-free survival. The t-test was used for measures that were normally distributed, and the rank-sum test was used for measures that were not normally distributed; the chi-square test was used for between-group comparisons of count data, and the Fisher exact probability method was used when necessary.

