### 10.2 Analysis of Primary and Secondary Study Endpoints

#### Primary Endpoints

Overall survival time (in months): Overall survival curves were plotted using the Kaplan-Meier method; the difference in survival risk between the two groups was assessed using the Log-Rank test with 95% confidence intervals; multivariate analyses were performed using the Cox proportional risk model to assess the effect of subgrouping (surgical procedure) and other prognostic factors on the survival risk, and 95% confidence intervals were given for each factor. A multivariate analysis using the Cox proportional risk model was performed to assess the effect of grouping factors (surgical modality) and other prognostic factors on survival risk with 95% confidence intervals for each factor.

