#### Secondary endpoints

Disease-free survival time (in months): Disease-free survival curves were plotted using the Kaplan-Meier method; differences in the risk of disease-free survival between the two groups were assessed using the Log-Rank test with 95% confidence intervals; multivariate analyses were performed using the Cox proportional risk model to assess the effect of subgrouping factors (surgical procedure) and other prognostic factors on the risk of disease-free survival, with 95% confidence intervals for each factor. A multivariate analysis using the Cox proportional risk model was performed to assess the effect of grouping factors (surgical modality) and other prognostic factors on the risk of disease-free survival with 95% confidence intervals for each factor.

- Surgical evaluation indicators.
- Surgical time (unit: minutes), intraoperative bleeding (unit: ml), intraoperative blood transfusion (unit: ml): all quantitative data not conforming to normal distribution, calculate the median, 25% quartile, 75% quartile, the minimum value, the maximum value, and analyze the difference between the two groups by using the rank sum test.
- Incidence of intraoperative accidents: count data, using chi-square test to analyze the difference between the two groups.
- Lymph node dissection: the total number of lymph node dissection (unit: one) and the number of lymph node dissection at each station (unit: one) were non-normally distributed measurements, and the difference between the two groups was analyzed using the rank-sum test; the number of stations of lymph node dissection (intrapulmonary, hilar, and ipsilateral mediastinal lymph nodes) was count data, and the difference between the two groups was analyzed using the chi-square test. Differences between the two groups were analyzed using the chi-square test.
- Tumor R0 resection rate: count data, using the chi-square test to analyze the difference between the two groups.
- Perioperative, 30-day, and 90-day complication rates, and mortality rates: were count data, and differences between the two groups were analyzed using the chi-square test.
- Quality of Survival and Cardiorespiratory Function Evaluation at Admission, Discharge, 30 Days, and 90 Days
- Quality of Life Score SF-36 Scale: Percentage, as a non-normally distributed measure, use rank sum test to analyze the difference between the two groups.

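### The secondary objective is tied to having had a lobectomy, and the planned operation is never recorded, so planned lobectomies that end as pneumonectomy can drop out of the lobectomy results

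*Protocol*

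**What the plan says.** The secondary objective, worded alike in the abstract (1.1) and in section 4, asks about perioperative and long-term outcomes in patients who were assessed for pneumonectomy at diagnosis and then "switched to neoadjuvant or induction chemoimmunotherapy and subsequent lobectomy". Having the lobectomy is part of the definition; planning one is not.

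Section 2.4.2 (assessment of risks and benefits) tells the surgeon to "take frozen pathology to clarify the status of the nearest incision margins during the surgery to decide the actual surgical method". Section 7.1.1 lists the operations in this single arm as "pneumonectomy, lobectomy, combined lobectomy, and sleeve lobectomy". It provides for a multidisciplinary reassessment of surgical feasibility after drug treatment, but does not ask that the operation then intended be written down. The visit schedule in 7.5 has no such item either.

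Section 10.1 uses a Cox model to "assess the effect of subgrouping (surgical modality) and other prognostic factors on survival and disease-free survival", and 10.2 repeats this for overall survival. For safety, 10.2 reads "Perioperative, 30-day, and 90-day complication rates, and mortality rates: were count data, and differences between the two groups" and applies a chi-square test. Operating time, blood loss, SF-36 and lung function are also compared between two groups. The groups are not defined anywhere in the protocol.

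**The concern.** A surgeon who adopts this strategy can choose to attempt a lobectomy but cannot choose to achieve one. The patient whose margin proves positive, and who leaves theatre with a pneumonectomy, is part of the price of trying. If results are reported for patients who ended with a lobectomy, that patient is missing from them. If the comparison is lobectomy against pneumonectomy, the same patient may be counted on the other side.

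Group membership would then depend on an intraoperative finding that is itself prognostic, because a positive margin means residual tumour where tissue was to be kept. Operating time, blood loss, complications, mortality, recovery and survival would all be open to a bias in favour of conversion. The protocol's own question is whether conversion is feasible and safe.

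**Working it through.** The protocol states no figure to reproduce. Section 5.3 sets 50 patients without a hypothesis. The check is therefore an illustration of direction and size.

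**Inputs from section 2.2** (propensity-matched comparison published in 2022): complications of grade III or higher, 13% after lobectomy and 21% after pneumonectomy; 90-day mortality, 1.9% and 6.9%.

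**Assumptions, not in the protocol:** of 50 patients, 40 are planned for lobectomy and 10 for pneumonectomy; k of the 40 end as pneumonectomy (k = 3, 5, 8); these k patients have complication rate r.

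**Formulas**
- By operation performed: lobectomy = 13%; pneumonectomy = (10 × 0.21 + k × r) / (10 + k).
- By operation planned: lobectomy = ((40 − k) × 0.13 + k × r) / 40; pneumonectomy = 21%.

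**Failed attempts at the cited pneumonectomy rate, r = 21%.** The pneumonectomy figure stays at 21% either way, so the difference by operation performed is 8.0 points. By operation planned, the lobectomy rate is 0.13 + k × 0.08 / 40:

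| k | Lobectomy, planned | Difference, planned | Shift from 8.0 |
|---|---|---|---|
| 3 | 13.6% | 7.4 | 0.6 |
| 5 | 14.0% | 7.0 | 1.0 |
| 8 | 14.6% | 6.4 | 1.6 |

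**Failed attempts with excess risk.** Take k = 5 and r = 30%.
- Performed: (2.1 + 1.5) / 15 = 24.0%, so the difference is 11.0 points.
- Planned: (4.55 + 1.5) / 40 = 15.1%, so the difference is 5.9 points.
- The shift is 5.1 points, of which 1.0 is already present at r = 21%. The other 4.1 come from the assumed excess.

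**90-day mortality, failed attempts at 6.9%.** All planned lobectomies: 1.9% + 5.0% × k/40. This gives 2.3% at k = 3 and 2.9% at k = 8, against 1.9% if only completed lobectomies count.

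**Direction.** The lobectomy figure is understated whenever r exceeds 13%. The difference between groups is inflated when r exceeds (9.7 + 0.13k) / (50 + k), found by setting the shift to zero. That is 19.0% at k = 3 and 18.5% at k = 8, so r at the cited 21% or above suffices.

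**Against sampling error.** With 40 and 10 patients, the standard error of the difference is √(0.13 × 0.87/40 + 0.21 × 0.79/10) = √(0.0028 + 0.0166) = 0.139, or 13.9 points.

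**The case against.** The strongest reply is that the protocol never says outcomes are assigned to the operation performed. A reader might infer that from the objective and from section 10, but the text does not settle it. Surgical modality and the two groups are undefined. Section 7.1.1 also divides surgery into open and minimally invasive, so the grouping could mean that. This stands, and the effect on the comparator is therefore conditional.

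Second, the secondary endpoints in 5.2 and 9.1 are not restricted to lobectomy, and 5.1 has outcomes recorded in the cohort as a whole. Whole-cohort figures would keep failed attempts in. This also stands, but such figures mix planned lobectomies with planned pneumonectomies and do not answer the objective as worded.

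Third, a positive frozen section may lead to a combined or sleeve lobectomy rather than a pneumonectomy, so crossovers could be few. That is true, and their number cannot be known from the protocol.

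Fourth, the bias is small beside chance. In the case with k = 5 and r = 30%, the lobectomy group gains 1.5 − 5 × 0.13 = 0.85 of an event in 40 patients. That limits the weight of the point. It does not make the narrower reporting set the better one.

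Fifth, a statistical analysis plan could define the sets. But the objective's population is fixed in the protocol, and no later document can reliably recover an intention that was not recorded before incision.

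**Conclusion.** The point holds in a limited form. Following the secondary objective as written leaves out planned lobectomies that end as pneumonectomy. If the groups in section 10 are lobectomy and pneumonectomy, those patients may be added to the comparator. With failed attempts at or above the cited pneumonectomy risk, this favours conversion.

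On the protocol's cited complication rates the shift is 0.6 to 1.6 points. This assumes a 40/10 split and 3 to 8 failures, and borrows rates from other patients. A reader might infer a distortion of 5 points or more. The protocol does not support that, because it requires failed attempts to carry a risk above 21% and no section gives such a figure. Nor does the text support the flat statement that outcomes are analysed by operation performed.

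The change is still worth making: it is cheap, it suits the question asked, and it cannot be made reliably after surgery.

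**What to change.** At the post-treatment multidisciplinary reassessment in 7.1.1, enter the planned operation on the case report form before incision, in two categories: lobectomy of any type, or pneumonectomy.

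Reword the secondary objective (1.1 and section 4) and 10.2 so that perioperative, recovery and survival outcomes are reported first for all patients with a planned lobectomy, whatever operation resulted. Use the planned operation alone to define this set. A set of attempted lobectomies would differ, since a patient may be found unsuitable on exploration before any attempt. Give results by operation performed as supportive, and state in 10.2 which two groups each comparison means.

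The cost is one field and changed wording. The figures for the lobectomy strategy may look slightly less favourable. No surgical rule changes.

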## 5. Research design

### 5.1 Overall design

In this single-arm, open-label, multicenter, prospective clinical trial, 50 cases of operable non-small-cell lung cancer requiring pneumonectomy were proposed to be enrolled. Patients will be treated with neoadjuvant or inductive combination therapy of immuno- and chemo- by evaluation from multidisciplinary discussion (Department of Thoracic Surgery, department of Respiratory Medicine, department of Radiology), than undergo open or minimally invasive radical surgery for lung cancer and systematic lymph node dissection. Peri-operative complications, lymph node dissection, R0 resection rate, and postoperative short-term and long-term efficacy outcomes will be recorded and evaluated.

Participating centers:

- 1 Ruijin Hospital, Shanghai Jiao Tong University School of Medicine, Shanghai, China
- 2 Shanghai General Hospital of Shanghai Jiao Tong University School of Medicine
- 3 The Ninth People's Hospital of Shanghai Jiao Tong University School of Medicine
- 4 Huadong Hospital, Fudan University Medical College, Shanghai, China

### 5.2 Defining study endpoints

The study is completed if the subject completes all phases of the study according to the protocol, if he or she is no longer being examined, or if the last subject has had the last follow-up visit.

A subject completes the study if he or she completes all phases of the study, including the last follow-up visit or the last treatment or examination specified in the protocol.

#### Primary study endpoints

- Tumor R0 resection rate (lobectomy)

#### Secondary study endpoints

- Overall survival (OS, unit:month)
- Disease-free survival (DFS, unit: month)
- Surgical Evaluation Indicators.
  - Surgical time (unit: minutes), intraoperative bleeding (unit: ml), intraoperative blood transfusion (unit: ml)
  - Incidence of intraoperative accidents
  - Lymph node dissection: total number of lymph node dissection (unit: one), number of lymph node dissection stations (intrapulmonary,hilar and ipsilateral

mediastinal lymph nodes), and the number of lymph nodes cleared at each station (unit: one).

- Perioperative, 30-day, 90-day complication rates, mortality rates
- Quality of Survival and Pulmonary Function Evaluation at Admission, Discharge, 30 Days, and 90 Days
  - Quality of Life Score: Scored using the short form-36 (SF-36) and recorded on a 100-point scale.
  - Resting oxygen saturation (unit: percentage)
  - Lung function: Tidal volume, Vital capacity, Forced vital capacity, first second vital capacity.
  - Tidal volume, Vital capacity, Forced Expiratory Volume In 1s, all in ml.

### **5.3 Determination of sample size**

This study is a prospective observational clinical study, and the purpose of the study is to evaluate the feasibility and long-term outcome of pneumonectomy to lobectomy after neoadjuvant or induction chemoimmunotherapy for locally progressive non-small cell lung cancer. Due to the lack of previous reference data, the sample size was not calculated based on hypothesis testing, and 50 patients were enrolled.

## **6 Study population**

### **6.1 Inclusion criteria**

The study subjects should meet the following criteria:

- 1) The patients voluntarily participate in the study, have good compliance, can cooperate with the requirements of the experiment to complete the observation and follow-up, and sign the informed consent form.
- 2) Aged over 18 years old, under 75 years old; male and female are not limited;
- 3) Pathologically confirmed non-small cell lung cancer with clinical stage T2-4N0-2, resectable non-small cell lung cancer, potentially needing pneumonectomy and receiving neoadjuvant or induction therapy.
- 4) ASA score: Grade I-III;
- 5) The cardiopulmonary function evaluation can meet the requirements for radical lung cancer surgery, and the liver and kidney functions are normal.

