**Study Objective :**

Primary objective: to investigate the feasibility of switching to lobectomy after neoadjuvant/induced chemoimmunotherapy in patients with operable non-small cell lung cancer requiring pneumonectomy at first diagnosis (R0 resection rate of lobectomy).

Secondary objective: to investigate the perioperative and long-term outcomes of patients with operable non-small cell lung cancer who were evaluated to undergo pneumonectomy at first diagnosis and switched to neoadjuvant or induction chemoimmunotherapy and subsequent lobectomy.

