**Study population:**

50 cases

- 1) Patients voluntarily participated in this study, had good compliance, could cooperate with the trial requirements to complete observation and follow-up, and signed the informed consent form;
- 2) Be over 18 and under 75 years of age, and is open to both men and women;
- 3) Pathologically confirmed non-small cell lung cancer and clinical stage T2-4N0-2, potentially need pneumonectomy, neoadjuvant, or induction Chemo-immunotherapy
- 4) ASA rating: I-III.
- 5) Cardiac function assessment was adequate for radical lung cancer surgery with normal liver and kidney function.

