## **9. Evaluation of study outcomes**

### **9.1 Evaluation of primary and secondary outcomes**

#### Primary Study Endpoints

R0 Resection rate (lobectomy): the proportion of patients with complete tumor removal by lobectomy, as evaluated by the pathologic findings of postoperative lung cancer specimens;

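### Inclusion criterion 3 admits patients who only potentially need pneumonectomy, while the objectives concern patients who require it at first diagnosis, and no recorded pre-therapy judgement of actual need is called for

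*Protocol*

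**What the plan says.** **Eligibility.** Criterion 3 in section 6.1 takes patients "potentially needing pneumonectomy and receiving neoadjuvant or induction therapy". The abstract (section 1.1, Study population) has the same qualifier: "potentially need pneumonectomy, neoadjuvant, or induction Chemo-immunotherapy".

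**Objectives and design.** The primary objective in section 4 concerns patients "who are required to undergo pneumonectomy at first diagnosis", and section 1.1 agrees. The secondary objective in both places concerns patients "who were evaluated to undergo pneumonectomy at first diagnosis". Section 5.1 states that "50 cases of operable non-small-cell lung cancer requiring pneumonectomy were proposed to be enrolled".

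**Endpoint.** Section 9.1 defines the primary endpoint as "the proportion of patients with complete tumor removal by lobectomy", judged on the postoperative specimen. It does not say among which patients the proportion is taken.

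**Procedures before therapy.** The schedule in section 7.5 puts the inclusion/exclusion check and a chest CT at screening. Section 11.5.1 has the eligibility criteria checked again in the data audit. Section 7.1.1 has bronchoscopy and enhanced chest CT completed, then a multidisciplinary discussion on giving chemoimmunotherapy. Surgical feasibility is discussed again after therapy.

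**The concern.** The trial asks how often a patient who needed a pneumonectomy can have a complete resection by lobectomy after chemoimmunotherapy. There is no control arm. What makes an R0 lobectomy a conversion is therefore only the fact that the patient needed pneumonectomy beforehand.

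Criterion 3 does not secure that fact. A patient for whom pneumonectomy was merely possible, and who could have had lobectomy from the start, satisfies it and would be scored as a success. If such patients do better than those who truly needed pneumonectomy, the reported rate overstates conversion, and enrolling more patients would not reduce the error.

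A prospective judgement cannot be recreated once therapy has begun. Baseline images and bronchoscopy findings could be re-read, but that gives a retrospective judgement, made with knowledge of the outcome unless the reader is blinded. Section 5.3 sets no hypothesis test or threshold for the sample size, so what is at stake is the estimate and its interpretation, not a formal decision.

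**Working it through.** **Step 1: the passages side by side.**

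| Place in Protocol | Need for pneumonectomy |
|---|---|
| 1.1 Study population, item 3; 6.1, item 3 | potential |
| 1.1 and 4, primary objective | required at first diagnosis |
| 1.1 and 4, secondary objective | evaluated for it at first diagnosis |
| 5.1 Overall design | required |
| 7.5 schedule, screening | inclusion check, hence potential need as worded in 6.1 |
| 7.1.1, discussion before therapy | decides on chemoimmunotherapy; extent of resection not mentioned |

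The rule that decides who enters is wider than the population named in the objectives. The screening check cannot narrow it, because it checks the rule as written.

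**Step 2: the plan's own figure.** There is none to reproduce. Section 5.3 says the 50 patients were not derived from hypothesis testing, and no passage gives the share of enrolled patients who would not have needed pneumonectomy.

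**Step 3: illustration of the possible shift.** All inputs are assumed. All enrolled patients are taken as the denominator.

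- q = share of enrolled patients who never needed pneumonectomy
- s = R0-lobectomy rate in that share
- p = R0-lobectomy rate in those who did need it

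Observed rate = q·s + (1 − q)·p, so the shift is q·(s − p).

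For q = 0.20 and p = 0.50: with s = 0.95, 0.19 + 0.40 = 0.59; with s = 1.00, 0.20 + 0.40 = 0.60. In the same way, for s from 0.95 to 1.00:

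| q | p = 50% | p = 70% | p = 90% |
|---|---|---|---|
| 10% | 54.5-55% | 72.5-73% | 90.5-91% |
| 20% | 59-60% | 75-76% | 91-92% |
| 30% | 63.5-65% | 77.5-79% | 91.5-93% |

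The direction depends on s > p. With s = 0.80 and q = 0.20, a true 50% reads as 56%, 70% as 72%, and 90% as 88%, so in the last case the bias is downward.

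**Step 4: scale.** Exact (Clopper-Pearson) 95% limits at n = 50, and the shift at q = 0.20 with s from 0.95 to 1.00:

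| Result | 95% limits | Half-width (points) | Shift (points) | Shift / half-width |
|---|---|---|---|---|
| 25/50 | 35.5-64.5% | 14.5 | 9-10 | 0.62-0.69 |
| 35/50 | 55.4-82.1% | 13.4 | 5-6 | 0.37-0.45 |
| 45/50 | 78.2-96.7% | 9.2 | 1-2 | 0.11-0.22 |

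**The case against.** **Need is already considered before therapy.** Criterion 3 is checked at screening and again in the data audit. Bronchoscopy and enhanced CT precede the pre-therapy discussion. Section 2.1 names invasion of the main pulmonary artery and main bronchus as the setting in which pneumonectomy is preferred. Section 2.4.2 prescribes frozen sections "In cases of main pulmonary artery invasion prior to neoadjuvant therapy", which presupposes that the original anatomy is known. This stands, and it limits the point. A reader might infer that nobody judges the need for pneumonectomy before treatment; the protocol does not support that. What is missing is narrower: a recorded statement that pneumonectomy is actually required, with the reason. Section 2.1 is background and the frozen-section instruction guides the operation, so neither supplies that record.

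**Need is always a prediction.** Section 2.4.2 lets frozen margins decide the operation, so *potentially* may be ordinary caution or loose wording. That is fair for the operation after therapy. The objectives, however, are anchored at first diagnosis. A reader might also infer that the sponsor means to enrol patients suitable for lobectomy. Nothing says so, and section 5.1 points the other way. The criterion merely fails to exclude them.

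**Timing of enrolment.** The word *receiving* in criterion 3, and the advice in section 2.4.2 to select patients with good results of therapy, might be read as enrolment of responders after treatment. Sections 5.1 and 7.1.1 place enrolment before therapy, and section 2.4.2 lists that selection as a risk-minimising measure for surgery. That reading is not supported.

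**The size is assumed.** This is correct. Each 20%-share shift in step 4 is smaller than the interval half-width at n = 50. If the endpoint is meant among lobectomies only, the true rate is probably high and the shift small.

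**Some material is not available.** The roadmap and intervention figures, the text between sections 2.4.2 and 4, and the CRF could not be read. They might contain such a record, but the conflict in wording would remain.

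**Conclusion.** The point holds in this form: the eligibility wording is wider than the population of the objectives and design, and no available passage requires a recorded pre-therapy judgement that pneumonectomy is required. In a single-arm trial scored on R0 lobectomy, this lets patients who never needed pneumonectomy count as conversions.

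The bias is upward only if those patients succeed more often than the rest. Its size cannot be determined from the protocol. The illustrated shifts run from about 15 points upward (30% share, true rate 50%, full success in that share) to 2 points downward (20% share, true rate 90%, 80% success). They rest on an assumed share, assumed success rates and an assumed denominator. They show that the effect could matter, not that it will. Because the remedy is cheap and must be in place before each patient's therapy begins, the change should be made.

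**What to change.** 1. Reconcile criterion 3 in sections 6.1 and 1.1 with the population stated in sections 1.1, 4 and 5.1.
2. Add one CRF item, completed for every patient before the first cycle of chemoimmunotherapy, at the discussion that section 7.1.1 already plans: whether pneumonectomy is judged required (yes / uncertain / no), and the anatomical reason. The clinical criteria for that judgement are for the sponsor to set.
3. If the wider criterion is kept, report the primary endpoint separately for patients judged at baseline to require pneumonectomy.

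**Cost.** Two wording changes and one CRF item; no examination is added or moved. If the criterion is tightened, some borderline patients are lost and accrual to 50 may be slower. If it is kept, accrual is unchanged but the estimate in the group of interest is less precise. For example, if 40 of the 50 patients were judged to require pneumonectomy (a 20% share removed), the interval would be wider by a factor of about √(50/40) = 1.12 at the same rate.
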